## 5.6. **Post-Imaging Prostatectomy**

Prostatectomy and pelvic nodal dissection will be performed at the discretion of referring physician after reviewing imaging results. Nodal dissection should follow standard of care.

- 5.6.1. **Negative imaging.** Subjects without evidence of positive nodal or metastatic disease on  $^{68}\text{Ga}$  PSMA-HBED-CC PET imaging will undergo radical prostatectomy and pelvic nodal dissection. The pelvic nodal dissection will be performed regardless of imaging results.
- 5.6.2. **Positive imaging.** The urologist will be informed of the location of any  $^{68}\text{Ga}$  PSMA-HBED-CC PET positive (or suspicious) regional pelvic nodes prior to surgery. The surgeon should attempt to capture the suspicious node during the nodal dissection.
- 5.6.3. **Nodal dissection.** Nodes will be marked by location using the standard procedures. For example, if the urologist removed left and right nodal regions separately, the subject will have two nodal regions (left/right). If the nodes are removed in six groups (bilateral internal/external/obturator nodes), the subject will have six nodal regions analyzed.
- 5.6.4. **Pathology:** Specimens from prostatectomy will be evaluated for the presence of nodal metastasis. This will be reported on a per patient basis, and by region as positive or negative. The pathology report should list the number of nodes counted during the exam.
- 5.6.5. **Immunohistochemical staining (IHC) (optional).** Although not routinely performed during standard practice, IHC staining for PSMA of tumor specimens (primary and lymph node metastases) is preferred.

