## 12.2. Reference standard definition:

12.2.1. Histopathology/Biopsy will be the primary determinate of tissue positivity and negativity for prostate cancer disease. Pathology date, organ, and location as well as any notes related to the pathology will be obtained from the subject chart. The anatomical region/sub-region the pathology occurred in will be assigned by the investigator team:

Ga-PSMA-HBED-CC positive findings are aimed to be confirmed by histopathology/biopsy if clinically feasible. Pathology performed 60 days before or after the Ga-PSMA-HBED-CC PET will be available for correlation.

Histopathological procedures and biopsies will be performed as clinically indicated and as per institutional protocol.

12.2.1.1. Lymph Nodes, Visceral Lesions, and Bone Lesions positive for disease by pathology.

- Lesions with positive pathologic confirmation will be regarded as positive for disease. The regionality of the resected tissue will be assigned into respective regions and sub-regions as described above in Table 12.2.

12.2.1.2. Lymph Nodes and Visceral Lesions negative for disease by pathology.

- Tissue removed and negative for pathology are considered negative for prostate cancer disease, unless subsequent conventional imaging or Ga-PSMA-HBED-CC PET imaging demonstrates that targeted tissue were not resected. In this case:

- i. Subjects can be rescanned with dedicated CT, MRI, or Ga-PSMA-HBED-CC PET/CT to determine if the suspicious Ga-PSMA-HBED-CC tissue was removed. If the tissue is confirmed as removed, this is considered negative for disease.

ii. If  $^{68}\text{Ga}$ -PSMA-HBED-CC PET/CT positive tissue is still present, a needle biopsy can be pursued at the discretion of the treating physician. Images of the procedure will be reviewed to determine if the correct tissue was biopsied.

- If the  $^{68}\text{Ga}$ -PSMA-HBED-CC PET/CT positive tissue was biopsied, a negative pathologic finding of the biopsied tissue is considered negative for disease.
- If the  $^{68}\text{Ga}$ -PSMA-HBED-CC PET/CT positive tissue was biopsied, a positive pathologic finding of the biopsied tissue is considered positive for disease.
- If biopsy or re-biopsy is not performed, or the wrong tissue was biopsied, change in node size as measured by conventional imaging and as defined below will be the criteria by which disease status will be defined.

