13.3.1. True positive region

13.3.1.1.  **$^{68}\text{Ga}$  PSMA-HBED-CC PET/CT positive for extra-pelvic node metastases by internal blind reader** – and pathology (if available) positive for that node, or, extra-pelvic node positive for disease by imaging as defined in Section 12.2.2.1.

13.3.1.2.  **$^{68}\text{Ga}$  PSMA-HBED-CC PET/CT positive for visceral metastases by internal blind reader** – and pathology (if available) positive for that visceral lesion, or, visceral lesion positive for disease by imaging as defined in Section 12.2.2.2.

13.3.1.3.  **$^{68}\text{Ga}$  PSMA-HBED-CC PET/CT positive for osseous metastases by internal blind reader** - and pathology (if available) positive for that osseous lesion, or, osseous lesion

positive for disease by imaging as defined in Section 12.2.2.3.

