13.3.2. True negative region

13.3.2.1.  **$^{68}\text{Ga}$  PSMA-HBED-CC PET negative for extra-pelvic node metastases by internal blind reader** – and pathology (if available) negative for disease, and, extra-pelvic node not positive for disease by imaging.

13.3.2.2.  **$^{68}\text{Ga}$  PSMA-HBED-CC PET negative for visceral metastases by internal blind reader** – and pathology (if available) negative for disease, and, visceral lesion not positive for disease by imaging.

13.3.2.3.  **$^{68}\text{Ga}$  PSMA-HBED-CC PET negative for osseous metastases by internal blind reader** - and pathology (if available) negative for disease, and, osseous lesion not positive for disease by imaging.

13.3.3. False positive region:

13.3.3.1.  **$^{68}\text{Ga}$  PSMA-HBED-CC PET positive for extra-pelvic nodes by internal blind reader**, pathology (if available) is negative, and imaging after prostatectomy demonstrates that node is not positive for disease.

13.3.3.1.1.  **$^{68}\text{Ga}$  PSMA-HBED-CC PET positive for regional node by internal blind reader**, but pathology (if available) is positive for node but in a different nodal region than the node seen on PSMA PET.

13.3.3.2. **PSMA-HBED-CC PET positive for visceral lesion by internal blind reader**, pathology (if available) is negative, and imaging after prostatectomy demonstrates that the visceral lesion is not positive for disease.

13.3.3.2.1.  **$^{68}\text{Ga}$  PSMA-HBED-CC PET positive for visceral lesion by internal blind reader**, but pathology (if available) is positive for visceral lesion but in a different region than the visceral region seen on PSMA PET.

13.3.3.3.  **$^{68}\text{Ga}$  PSMA-HBED-CC PET positive for osseous lesion by internal blind reader**, pathology (if available) is negative, and imaging after prostatectomy demonstrates that the osseous lesion is not positive for disease

13.3.3.3.1.  **$^{68}\text{Ga}$  PSMA-HBED-CC PET positive for osseous lesion by internal blind reader**, but pathology (if available) is positive for osseous lesion but in a different region than the osseous region seen on PSMA PET.

13.3.4. False negative region:

13.3.4.1.  **$^{68}\text{Ga}$  PSMA-HBED-CC PET negative for extra-pelvic nodes**

by internal blind reader, and pathology (if available) positive for that node, or, extra-pelvic node positive for disease by imaging as defined in Section 12.2.2.1.

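### The main false-positive rules for distant disease require imaging after prostatectomy but the true-positive and true-negative rules do not, so men left unoperated after PET can bias secondary PPV and specificity upward

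*Combined protocol and SAP*

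**What the plan says.** Section 13.3 of the combined protocol and SAP classifies each distant region by cell.

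- **False positive.** The main rules need a positive PET, negative pathology where it exists, and a further imaging condition. For extra-pelvic nodes (13.3.3.1) it is "imaging after prostatectomy demonstrates that node is not positive for disease", for viscera (13.3.3.2) "imaging after prostatectomy demonstrates that the visceral lesion is not positive for disease", and for bone (13.3.3.3) "imaging after prostatectomy demonstrates that the osseous lesion is not positive for disease".
- **False positive, sub-rules.** A second route has no surgery condition. For viscera (13.3.3.2.1) it applies when PET is positive "but pathology (if available) is positive for visceral lesion but in a different region than the visceral region seen on PSMA PET"; for bone (13.3.3.3.1), "but pathology (if available) is positive for osseous lesion but in a different region than the osseous region seen on PSMA PET". The node version (13.3.3.1.1) is worded for a regional node.
- **True positive.** A PET-positive extra-pelvic node needs only "pathology (if available) positive for that node, or, extra-pelvic node positive for disease by imaging as defined in Section 12.2.2.1" (13.3.1.1). The visceral and osseous rules are parallel. Neither these nor the true-negative rules (13.3.2) mention surgery.
- **Non-evaluable.** A region that fits none of the four cells leaves the table (13.3.5.1).

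On surgery, Section 5.6 states: "Prostatectomy and pelvic nodal dissection will be performed at the discretion of referring physician after reviewing imaging results". Section 13.2.5.2 takes men with extra-pelvic nodal metastases who are not operated on out of the primary analysis. Section 13.3 has no such exclusion.

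On the reference standard, 12.2.1.2 says of biopsied PET-positive node or visceral tissue that "a negative pathologic finding of the biopsied tissue is considered negative for disease". For bone, 12.2.1.3 assigns negative status when pathology shows another diagnosis known to take up the tracer. Section 12.2.2 does not allow conventional imaging to establish that a region is negative.

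**The concern.** Whether a lung, liver or bone lesion is cancer does not depend on whether the prostate was removed. Yet in a man who is not operated on, a biopsy that confirms the PET finding is counted, while a biopsy that refutes it normally is not. Section 5.6.1 expects PET-negative men to go to surgery, so unoperated men will mostly be those with positive scans, which are the scans that supply the PPV denominator.

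PPV and specificity for distant disease are stated secondary objectives (1.2.1), and Section 2.4 says the data are meant to support further approvals of the agent. A rule that can discard false positives but not true positives makes those two figures hard to interpret.

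**Working it through.** **The plan's own figures.** The documents state no expected PPV and no rate of cancelled surgery. The only design figure is the table of 95% half-widths for sensitivity at n = 30 (13.1). It reproduces with 1.96 × √(p(1−p)/30): 16.40, 15.49, 14.31, 12.78 and 10.74%, against the stated 16.4, 15.5, 14.3, 12.8 and 10.7%. It does not bear on this point.

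**Tracing the rules.** Take a man with a PET-positive liver lesion whose prostatectomy does not go ahead.

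| Biopsy of the lesion | Status under Section 12 | Cell under 13.3 |
|---|---|---|
| Positive | Positive (12.2.1.1) | True positive (13.3.1.2) |
| Negative, no positive pathology elsewhere | Negative (12.2.1.2) | 13.3.3.2 not met, so non-evaluable (13.3.5.1) |
| Negative, with a positive visceral lesion in another region | Negative (12.2.1.2) | False positive (13.3.3.2.1) |

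An extra-pelvic node follows the first two rows; the third is doubtful because 13.3.3.1.1 speaks of a regional node. Bone follows the same pattern, except that its negative status comes from 12.2.1.3, when pathology shows a known PSMA-positive alternative diagnosis.

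**Direction.** The condition removes regions from the false-positive cell only. True positives and true negatives are untouched, so TP/(TP+FP) and TN/(TN+FP) can rise or stay the same but cannot fall.

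**Size, by counts (assumed).** With 7 true-positive and 3 false-positive regions, PPV is 7/10 = 70.0%. Losing one false positive gives 7/9 = 77.8%; losing two gives 7/8 = 87.5%. With an assumed 20 true negatives, specificity moves from 20/23 = 87.0% to 20/22 = 90.9% or 20/21 = 95.2%.

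**Size, in general.** Let p be the PPV with the surgery condition removed. Let c be the share of *false-positive* regions that lie in unoperated men and are not caught by the different-region sub-rules. Then

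apparent PPV = p / (p + (1 − p)(1 − c)).

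Both inputs are assumptions:

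| p | c = 0 | c = 0.25 | c = 0.50 | c = 0.75 |
|---|---|---|---|---|
| 50% | 50% | 57.1% | 66.7% | 80.0% |
| 70% | 70% | 75.7% | 82.4% | 90.3% |
| 90% | 90% | 92.3% | 94.7% | 97.3% |

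The sub-rules lower c. If half of the false-positive regions are in unoperated men and a quarter of those are caught, c = 0.5 × 0.75 = 0.375, and 70% becomes 0.70/(0.70 + 0.30 × 0.625) = 78.9%.

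**The case against.** **Unoperated men are not shut out of the false-positive cell.** A reader might infer that they can never be false positives, or that PPV must be 100% if every man with distant findings goes unoperated. The documents do not support this for viscera and bone, because 13.3.3.2.1 and 13.3.3.3.1 work without surgery. If all false-positive regions were in unoperated men and the sub-rules caught a quarter, c = 0.75 and a 70% PPV would read 90.3%. Only for extra-pelvic nodes, on a literal reading of 13.3.3.1.1, might the cell be closed. The route is narrow, however, and does not help the plain biopsy-negative lesion.

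**The share of all PET-positive regions in unoperated men does not give the bias.** It would do so only if PPV were equal in operated and unoperated men. As an assumed example, put half of the regions in unoperated men with PPV 90%, and half in operated men with PPV 50%. Overall PPV is 70%, but false positives lost are 5 of 30 points, so apparent PPV is 0.70/0.95 = 73.7%, not 82.4%. This stands, and is why c above refers to false-positive regions.

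**The larger obstacle is 12.2.2.** An unbiopsied lesion that is not positive on imaging is indeterminate there, so the imaging limb of 13.3.3 conflicts with Section 12 for operated men too. This also stands. It shapes the fix but does not remove the asymmetry for biopsied lesions.

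**The biopsy sentence in 12.2.1.2 has a narrower setting.** It sits in the step for tissue still present after earlier negative pathology. That is correct, but 12.2.1 makes pathology the primary determinant of both positive and negative status, and 12.2.1.2 opens with the same principle for removed tissue.

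**The phrase may be carried over and the stakes modest.** It fits primary rule 13.2.3.1, where imaging checks that a pelvic node was removed, and an analyst might ignore it here. But the plan should not depend on that. The endpoint is descriptive, in a 30-patient pilot used mainly to plan around sensitivity. This limits the seriousness of the point but not its correctness.

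**Conclusion.** The point holds as an asymmetry in the cell definitions. In unoperated men, a biopsy-negative distant lesion that Section 12 treats as negative meets no main false-positive rule and drops out, while a biopsy-positive one is kept as a true positive. The effect on secondary PPV and specificity is upward or nil. It is nil if no false-positive region falls in an unoperated man, so the documents do not show that the figures *will* be inflated.

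The size cannot be fixed from the documents; the counts and tables above rest on assumed values of p and c. With few distant lesions likely to be classified among 30 patients, a change of one or two regions could move the estimates visibly. This should be corrected, but it does not touch the primary endpoint.

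**What to change.** 1. In 13.3.3.1, 13.3.3.2 and 13.3.3.3, delete the words *after prostatectomy*.
2. State that negative pathology of the PET-positive lesion under 12.2.1.2 (for bone, negative status under 12.2.1.3) is sufficient on its own for a false positive, whether or not prostatectomy was done.
3. For lesions without pathology, reconcile the imaging limb of 13.3.3 with 12.2.2, which bars conventional imaging from establishing negativity. Apply the resulting rule identically to operated and unoperated men, with timing counted from the PET scan. Pathology should not simply become the only route without settling this: that would drop the imaging-only false positives that 13.3.3 now allows and could itself raise PPV.
4. Report the number of non-evaluable PET-positive regions by surgery status.

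The cost is a wording change in three rules and one extra line in the results table, with no new data. The downside is that reported PPV and specificity may be lower.

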### 1.2. Secondary objective

- 1.2.1. Determine sensitivity, specificity, positive, and negative predictive value of  $^{68}\text{Ga}$  PSMA-HBED-CC PET for detection of extra-pelvic nodal metastases, visceral metastases, and osseous metastases compared to biopsy and imaging follow-up.

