## 12. EFFICACY ASSESSMENTS

Determination of efficacy requires two primary assessments.

The first assessment is the clinical read of the  $^{68}\text{Ga}$ -PSMA-HBED-CC PET/CT scan. Trained readers will identify lesions positive for prostate cancer disease, and based on these results, will categorize specifically defined anatomical regions of the subject (Table 12.2) as positive for disease by  $^{68}\text{Ga}$ -PSMA-HBED-CC PET/CT. Criteria are described in Section 12.1 below.

The second assessment is the reference standard determination of disease positivity or negativity also performed on the same specifically defined anatomical regions (Table 12.2). The reference standard definitions are described below, and consist of a combination of pathological confirmation, conventional imaging follow-up evidence, and serial PSA measurements. Criteria are described in Section 12.2 below.

For purposes of endpoints, four major regions are identified for final analysis as defined in Table 12.1. Each region is divided into subregions as defined in Table 12.2. All primary data from  $^{68}\text{Ga}$ -PSMA-HBED-CC PET interpretations, pathology results, and conventional imaging results, will be collected per the subregions defined below. The final region assignments and results will be derived from the subregion data as applicable.

Region	Description
1	Prostate Bed
2	Pelvis outside of prostate bed including lymph nodes
3	Extrapelvic soft tissue, lymph nodes and organ metastases (non-bone)
4	Bone metastases

Table 12-1. Major Analysis Regions

Region 2: Pelvis outside of prostate bed	Region 3: Extrapelvic soft tissue	Region 4: Bone metastases
Right obturator	Lung	Spine
Left obturator	Liver	Ribs
Right external iliac	Pancreas	Pelvis
Left external iliac	Spleen	Extremities
Right internal iliac	Intestine	Skull
Left internal iliac	Mesentary	Sternum
Other pelvic regions	Brain	Clavicle
	Other soft tissue	Other bone
	Abdominal nodes	
	Thoracic nodes	
	Other nodes	

Table 12-2. Subregion Classification

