## 13. STATISTICAL CONSIDERATIONS

### 13.1. Statistical Justification

This study is a pilot study to determine target sensitivity for Ga PSMA-HBED-CC for the detection of prostate cancer in the pre-prostatectomy population. Based upon literature, we anticipate sensitivities of > 80% in this patient population, but there are uncertainties, particularly related to the proposed reference standard. We plan to use the results of this pilot study, potentially combined with reported results from other sites across the US performing similar studies (same patient population, same methods, same reference standard definitions...) to determine most-appropriate primary endpoint sensitivities for a larger University of Iowa study to follow this one, so as to appropriately statistically power the larger study.

The primary objective of this pilot study is to obtain preliminary information on the sensitivity of physician reads for Ga-68 PSMA pre-prostatectomy; physicians' ability to correctly identify prostate cancer and metastases via Ga-68 PSMA relative to our pathology/conventional imaging reference standard. Due to the lack of clinical experience with this radiopharmaceutical, this pilot study is meant to gain meaningful information of the sensitivity of this agent in this patient population to generate hypotheses for further trials.

To evaluate sensitivity, patients must undergo both Ga-68 PSMA imaging and evaluation for prostate cancer by pathology, follow-up conventional imaging, or both. Sensitivity is defined as:

$$Sensitivity = \frac{\text{number of true positives (TP)}}{\text{number of true positives (TP)} + \text{number of false positives (FP)}}$$

The table below provides 95% confidence interval half-widths for a range of sensitivity values based on a planned sample size of 30 patients using a normal approximation.

Sensitivity	Half-Width
70%	16.4%
75%	15.5%
80%	14.3%
85%	12.8%
90%	10.7%

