### 13.3. Secondary Endpoints:

Analysis plan for Secondary Endpoints: We will report the sensitivity, specificity, positive and negative predictive value of  $^{68}\text{Ga}$  PSMA-HBED-CC PET/CT over all imaged regions as well as sub-classified by the following regions:

- extra-pelvic nodal metastases
- visceral metastases
- osseous metastases

No statistical significance will be generated due to the pilot nature of the project.

Follow-up for extra-pelvic nodal metastases, visceral metastases and osseous metastases are defined as below:

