13.3.4.2.  **$^{68}\text{Ga}$  PSMA-HBED-CC PET negative for extra-pelvic nodes by internal blind reader**, and pathology (if available) positive for that visceral lesion, or, visceral lesion positive for disease by imaging as defined in Section 12.2.2.2.

13.3.4.3.  **$^{68}\text{Ga}$  PSMA-HBED-CC PET negative for extra-pelvic nodes by internal blind reader**, and pathology (if available) positive for that osseous lesion, or, osseous lesion positive for disease by imaging as defined in Section 12.2.2.3.

13.3.5. Non-evaluable region:

13.3.5.1. Any region that does not have sufficient data to meet the criteria for definition of true positive region, true negative region, false positive region, or false negative region will be classified as non-evaluable.

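### Visceral and osseous false negatives are tied to the node read, and where pathology is missing Section 13.3 infers negativity from imaging that Section 12.2 bars for that use

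*Combined protocol and SAP*

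**What the plan says.** **False-negative rules.** Section 13.3.4 has one rule each for extra-pelvic nodes, visceral lesions and bone. All three open with the same PET condition, "PET negative for extra-pelvic nodes by internal blind reader". The reference half then changes by lesion type; for bone (13.3.4.3) it reads "and pathology (if available) positive for that osseous lesion, or, osseous lesion positive for disease by imaging as defined in Section 12.2.2.3". The other rules use the lesion's own read: the osseous true-positive rule (13.3.1.3) begins "PSMA-HBED-CC PET/CT positive for osseous metastases by internal blind reader", and 13.3.1.2, 13.3.2.2, 13.3.2.3, 13.3.3.2 and 13.3.3.3 follow the same pattern. Section 13.3.5.1 is the catch-all: "Any region that does not have sufficient data to meet the criteria" for any of the four classes is non-evaluable.

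**Negativity.** In 13.3.2 (true negative) and 13.3.3.1 to 13.3.3.3 (false positive), pathology counts only if it is available. Otherwise the class rests on the lesion not being positive on imaging. Section 12.2.2 bars conventional imaging from establishing that a region is negative, citing its low negative predictive value. Sections 12.2.2.1 iii, 12.2.2.2 iii and 12.2.2.3 iv call a region indeterminate when it is not positive on imaging and has no pathology.

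**Reporting.** Objective 1.2.1 asks for all four accuracy measures for extra-pelvic nodal metastases, "visceral metastases, and osseous metastases compared to biopsy and imaging follow-up". Section 13.3 reports them "over all imaged regions as well as sub-classified by the following regions", naming three distant classes.

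**The concern.** A region's class should follow from its own PET read and one reference standard. Here the PET half of two false-negative rules belongs to another lesion type, and the reference half of the true-negative and false-positive rules conflicts with the section that defines the reference standard. Two analysts working faithfully from different sections would report different secondary results from the same data.

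Section 13.3.2 also does not say whether not positive by imaging requires that imaging was done. Section 12.2.2 limits study follow-up imaging to subjects with positive PET findings, so a PET-negative node or visceral region could count as a true negative with no follow-up image.

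**Working it through.** **Inputs.** The plan gives no target or projected figure for the secondary endpoints, so there is none to reproduce. The only planning number used is the 30 patients in 13.1. All region counts below are assumptions, because the documents give no rates of distant metastasis or distant biopsy.

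**Formulas.** Sensitivity = TP/(TP+FN); specificity = TN/(TN+FP); PPV = TP/(TP+FP); NPV = TN/(TN+FN). Section 13.1 prints sensitivity with "number of false positives (FP)" in the denominator. That is a separate error and is not followed here.

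**Step 1: false-negative rules as written.** For a visceral or bone region with confirmed disease:

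| Own read | Node read | Rules met as written | Class intended |
|---|---|---|---|
| positive | positive | TP | TP |
| positive | negative | TP and FN | TP |
| negative | negative | FN | FN |
| negative | positive | none, so 13.3.5.1 | FN |

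Two of the four combinations fail.

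**Step 2: size of that failure.** Let S be the true sensitivity and q the share of confirmed regions with a positive node read, taken as independent of the region's own read.

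- If double-classified regions count in both cells, apparent sensitivity = S/(S + 1 − q). With S = 0.80: 0.80/1.80 = 44.4% (q = 0), 0.80/1.30 = 61.5% (q = 0.5), 0.80/1.05 = 76.2% (q = 0.75).
- If TP takes precedence, it is S/(S + (1 − S)(1 − q)): 80.0%, 0.80/0.90 = 88.9% and 0.80/0.85 = 94.1%.

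The first reading understates sensitivity in these cases. The second overstates it once q exceeds 0, because only the dropped misses remain as an error. NPV moves similarly. With 84 true negatives and no miss, one double count gives 84/85 = 98.8% instead of 100%. With 80 true negatives and 4 detected misses, dropping one gives 80/83 = 96.4% instead of 80/84 = 95.2%.

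**Step 3: the two negativity rules on the same data.** Assume 30 patients × 3 distant classes = 90 regions: 4 PET-positive and confirmed, 2 PET-positive and imaged but not positive, 84 PET-negative, and no other pathology.

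| Rule | TN | FP | Specificity | PPV |
|---|---|---|---|---|
| 13.3, imaging not required for TN | 84 | 2 | 84/86 = 97.7% | 4/6 = 66.7% |
| 12.2 | 0 | 0 | not estimable | 4/4 = 100% |

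- If 13.3 is read to require imaging and 42 or 21 of the 84 were imaged, specificity is 42/44 = 95.5% or 21/23 = 91.3%.
- Pathology narrows the gap. With 10 PET-negative regions and 1 of the 2 unconfirmed PET-positive regions (node or visceral) sampled negative, 12.2 gives specificity 10/11 = 90.9% and PPV 4/5 = 80.0%. With both sampled negative, PPV is 66.7% under either section.
- For a single class, take 30 unsampled bone regions, none positive on imaging. With 1, 3 or 5 of them PET-positive, 13.3 gives specificity 29/30 = 96.7%, 27/30 = 90.0% or 25/30 = 83.3%. Under 12.2, none of the 30 is evaluable.

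**Step 4: unequal verification.** Suppose 4 of the 84 PET-negative regions are true misses and only 1 is found. Observed sensitivity is 4/5 = 80.0% against a true 4/8 = 50%. True NPV is 80/84 = 95.2%. Section 13.3 gives 83/84 = 98.8%; 12.2 gives 0/1 without pathology, or 10/11 = 90.9% with 10 sampled negatives. So NPV runs high under one rule and low under the other.

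**The case against.** **The false-negative wording is a slip with clear intent.** The reference halves name the visceral and osseous lesion, and every sibling rule uses the matching read. A sensible analyst would repair it, and nobody need count one region twice. That stands: the low figures in Step 2 arise only if double-classified regions count in both cells. But the text states no precedence, and a dropped miss remains even when TP takes precedence. Table 12-1 does merge nodes and organs in Region 3, "Extrapelvic soft tissue, lymph nodes and organ metastases (non-bone)", but bone is Region 4, so the merging cannot explain 13.3.4.3.

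**Imaging is meant to count.** Objective 1.2.1 names imaging follow-up, and 12.2.1.5 lets imaging help settle unsampled regions. Neither lifts the bar in 12.2.2, which confines imaging to establishing positivity. Section 12 places the reference criteria in 12.2. Rules 13.3.1 and 13.3.4 cite it for imaging positivity, while 13.3.2 and 13.3.3 cite no imaging-negative definition, because 12.2 has none.

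**Stronger readings that the documents do not support.**

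- A reader might infer that a negative biopsy of PET-positive bone has no class. Section 12.2.1.3 leaves it open, but 13.3 gives one: false positive if imaging is not positive (13.3.3.3), true positive if imaging is positive (13.3.1.3), otherwise non-evaluable (13.3.5.1).
- A reader might infer that PET-negative regions are checked only through PET-triggered imaging. Section 12.2.2 also tracks all subjects for standard-of-care imaging. For bone, 12.2.2.3 i accepts baseline findings, including the CT portion of the PET/CT, which every scanned subject has. The imaged-only denominators in Step 3 may therefore not apply to bone.
- A reader might infer that specificity cannot be estimated at all under 12.2. That holds only for unsampled distant classes. An overall analysis that includes the pelvis, where surgical patients have nodal pathology, would differ less.
- A reader might infer that every false-positive rule conflicts with 12.2. Rules 13.3.3.1.1, 13.3.3.2.1 and 13.3.3.3.1 rest on positive pathology in a different region and do not.

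**Conclusion.** Both parts hold as written and should be fixed before regions are classified. The first is a drafting error that can move secondary sensitivity and NPV in either direction, depending on how double-classified regions are counted. The second is a real conflict, confined to regions without pathology, that leaves specificity, PPV and NPV for the distant classes to the choice of section: 97.7% against not estimable for specificity, and 66.7% against 100% for PPV, in the assumed example. The percentages illustrate and do not forecast. The contradictions themselves do not depend on them.

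It would be wrong to conclude that the primary endpoint is compromised. Its true-negative rule (13.2.2.1) requires negative pathology, and its false-positive rule 13.2.3.1 uses imaging only to confirm that a node is gone. The sample size is also untouched, and 13.3 plans no significance testing.

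**What to change.** 1. In 13.3.4.2 make the PET condition a negative visceral read, and in 13.3.4.3 a negative osseous read.
2. Reconcile 13.3.2 and 13.3.3.1 to 13.3.3.3 with 12.2 so that one negativity rule governs. One workable choice is the 12.2 rule, with indeterminate regions sent to 13.3.5 and their number reported by class and PET result.
3. Report the other rule as a labelled sensitivity analysis, and state there that a region must have been imaged to count as negative.
4. State that in the 12.2-only analysis an unsampled PET-positive region can enter only as TP, which pushes PPV up, and an unsampled PET-negative region only as FN, which pushes NPV down. Neither should be interpreted where reference negatives come only from pathology.
5. State that study-triggered follow-up imaging is limited to PET-positive subjects, so PET-negative node and visceral regions are verified less often and sensitivity tends to be too high. Note that the baseline criteria in 12.2.2.3 i partly offset this for bone.
6. For biopsied bone, cross-refer 12.2.1.3 to 13.3.1.3, 13.3.3.3 and 13.3.5.1. No new rule is needed.

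The cost is protocol wording and one extra table, with no new data or visits. The drawback is fewer evaluable regions in the 12.2-based analysis, where specificity and NPV may rest on few regions or not be estimable.
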